11.6 Deviations from the statistical plan

Any deviation from the planned statistical analyses will be justified and detailed in the reports derived from the processing of the data.

11.7 Population under analysis

The population analyzed in the study will consist of all patients included in the study as detailed in the protocol and without major deviations from the protocol.

12. Direct Access to Source Data/Documents

The sponsor shall ensure that it is specified in the protocol or other written agreement that the investigator or institution shall allow direct access to the source data or documents for monitoring, auditing and review by the IRB as well as inspection of the trial by the competent health authorities.

13. Ethics

General considerations: The trial will be carried out in accordance with the principles emanating from the Declaration of Helsinki (See Annex *VIII*) and according to the legal regulations in force (Royal Decree 223/2004) and will not begin until the approval of the reference CEIC, the approval of the Management of all the participating centres, and the authorisation of the Spanish Agency for Medicines and Health Products have been obtained.

Information to the subjects: Patients will be informed orally and in writing and all relevant information adapted to their level of understanding will be communicated to the participants. (See *Attachment III: Patient Information Sheet/Written Consent Sheet*)

14. Data Management and Archiving of Records

The patient will be informed that their participation in the trial will be treated with the same confidentiality as their clinical documentation.

In the data collection notebook, the patient will be identified only by their inclusion code in the study.

The patient's name will not appear in any publication or communication of the results of the study.

The patient's participation in the trial will be reflected in their medical history.

The investigator will complete a list that will include the names of the patients participating in the trial, their inclusion number in the trial and their medical history.

Only researchers and data quality assurance and data analysis personnel will have access to the participant's clinical documentation. Eventually, persons duly authorised by the Sponsor and the Health Authorities and the Clinical Research Ethics Committee may audit or inspect the trial. Personal information will not be available to the public, in compliance with the provisions of Organic Law 15/1999, of 13 December, on the Protection of Personal Data.

Prior to the start of treatment, a clinical examination, electrocardiogram and blood and urine sample will be taken (*SEE TABLE OF DAILY DETERMINATIONS*).

The data will be collected through an online electronic CRD.

15. Financing and Insurance

The promoter has taken out civil liability insurance in accordance with current regulations.

16. Publication Policy

The Promoter undertakes to publish the results, both positive and negative, of this study as stated in art. 39 of RD 223/2004.

17. Table of examinations and treatment during follow-up

Treatment Visit Schedule														
Clinical Evaluations	Day 1	ST 2a	ST 4	ST 6	ST 8	ST 10	ST 12	ST 16	ST 20	ST 24	ST 30	ST 36	ST 42	ST 48/dFT
Inclusion and exclusion criteria	X													
Vital signs	X	X	X	X	X	X	X	X	X	X	X	X	X	X
Weight	X									X				X
Physical examination	X		X				X			X		X		X
Adverse events	X	X	X	X	X	X	X	X	X	X	X	X	X	X
Concomitant medications	X	X	X	X	X	X	X	X	X	X	X	X	X	X
Confirmation of the use of contraceptive methods by the patient and his or her partner	X	X	X	X	X	X	X	X	X	X	X	X	X	X
Simplified Compliance Questionnaire	X	X	X		X		X		X	X		X	X	X
Haematology	X	X	X	X	X	X	X	X	X	X	X	X	X	X
TP/TTP	X						X			X				X
Blood biochemistry (simplified, fasting)		X	X		X		X		X		X		X	
Blood biochemistry (complete, not fasting)	X			X				X		X		X		X
Thyrotropin (TSH)	X						X			X		X		X
Serum pregnancy test (women only)	X													X
Urine pregnancy test (women only)		X	X	X	X	X	X	X	X	X	X	X	X	X
Samples for pharmacogenetics	X													
HCV RNA CPR*	X		X		X		X			X				X

All laboratory specimens should be obtained prior to administration of the first dose of study medication.

- Samples will be obtained for a genotypic resistance test if the patient has >100 IU/mL at week 12 or later. A single blood sample will be obtained for genetic studies.

Complete blood biochemistry: ALT, AST, creatinine, alkaline phosphatase, gammaglutamyl transferase (GGT), total bilirubin (direct and indirect), total proteins, albumin, uric acid, urea nitrogen, glucose, HbA1C (patients diagnosed with diabetes, either receiving pharmacological treatment or controlled with diet), amylase, lipase, sodium, potassium, chloride, phosphorus, calcium, triglycerides, and cholesterol.

Simplified blood biochemistry: alanine aminotransferase (ALT), aspartate aminotransferase (AST), creatinine, alkaline phosphatase, total bilirubin (direct and indirect), urea nitrogen, total proteins, albumin, uric acid and glucose.

Fibrosis evaluation: This will be done by liver biopsy or Fibroscan. In patients without cirrhosis on histology or Fibroscan, evaluation must have been performed no more than 18 months prior. A result of 12 kilopascals or more on the Fibroscan test would allow the patient to be considered cirrhotic.

Ultrasound: Patients with bridge fibrosis or cirrhosis must have an ultrasound performed within 6 months prior to inclusion in the study.

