
5. Objective and Purpose of the Trial

Main:

The primary objective of this study is to evaluate the safety and efficacy of response-guided therapy with boceprevir 800 mg three times daily orally (o.v.) in combination with peginterferon (alpha-2b or alpha-2a) and ribavirin in genotype 1 HIV- and HCV-infected patients in whom prior HCV treatment with ribavirin-associated pegylated interferon had failed.

Side:

- To define predictors of sustained virologic response (SVR), such as epidemiological factors, disease characteristics, clinical status of HIV infection, and response during treatment, especially at weeks 4, 8, 12, and at the end of treatment.
- To determine the percentage of patients with undetectable HCV RNA at treatment weeks (ST) 4, 8, and 12 and at the end of treatment.
- To evaluate the virological response according to baseline characteristics.
- To investigate HCV resistance after virological failure with a boceprevir-containing regimen (BOC). Blood samples should be obtained at baseline, at the time of virological failure (VF) (VF: two consecutive samples with signs of HCV replication after HCV was undetectable – below the lower limit of detection – or HCV RNA rebound equal to or greater than one logarithmic unit with respect to the RNA nadir) and six months after virological failure. The evaluation of resistance will be carried out in a single center (coordinating center: Hospital Clínic, Barcelona) by means of population sequencing of the genome that encodes the HCV protease.

6. Trial Design

Open-label, Phase III, prospective, multicenter study.

6.1 Main and secondary variables:

Primary endpoint:

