6.3 Guidelines for BOC Dose Modification

The dose of BOC cannot be reduced in the study.

Grade 1 and 2 AEs require close follow-up but no change in treatment.

All grade 3 toxicities will be treated by the facility investigator as appropriate. Any grade 4 toxicity that, in the opinion of the centre's investigator, is directly related to BOC, will be treated with the permanent suspension of the latter.

In case of intolerance to the BOC, its administration will be suspended; The dose cannot be reduced. If BOC is temporarily or permanently stopped, patients may continue to receive PEG-IFN and RVB.

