8.2 Concomitant and rescue medication

Any concomitant medication must be reflected in the CRF in an appropriate way (detailing the product, dosage, route, days of administration, reason for treatment, etc.).

Treatments not allowed:

The administration of treatments that are contraindicated with the study drugs will not be allowed. (see annex technical sheets) and section 10 of the protocol

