10.3 Evaluation of toxicity parameters

The classification system for drug toxicity is set out in the DAIDS Table for Grading the Intensity of Adverse Events in Adults and Children, which can be found on the DAIDS RSC website: <http://rsc.techres.com/safetyandpharmacovigilance/>.

Treatment of PEG-IFN Side Effects

Side effects of PEG-IFN usually include flu-like symptoms such as myalgia, arthralgias, headache, chills, low-grade fever, nausea, vomiting, and tiredness, as well as erythema, pain, and edema at the injection site. Less common are side effects of the central nervous system (CNS), such as depression, insomnia, anxiety, and irritability. Abnormalities of thyroid function have been described, as well as neutropenia, thrombocytopenia, and alopecia. The decrease in neutrophil and platelet count is usually dose-dependent and usually reaches nadir by week 4. Reductions in the total number of white blood cells may also occur, although usually not below normal levels. In week 2, dose-related decreases have been observed for other analytical parameters, such as albumin, globulin, total proteins, potassium and calcium; however, most parameters normalize by week 4 of treatment. Inflammation at the injection site occurs intermittently throughout treatment, but usually does not limit it. In general, all these effects are reversed by decreasing or interrupting the dose; patients cannot continue to take RBV and BOC if PEG-IFN is permanently discontinued.

Treatment of IFN-associated neutropenia

Patients who develop neutropenia during treatment may receive G-CSF (not provided by the study) at the discretion of the center investigator.

Table 1. Treatment of toxicity: neutropenia

Parameter	Downward dose adjustment of PEG-IFN
RAN (cells/mm ³)	
Grade 1 (1,000- 1,300)	None

Grade 2 (750999)	No dose adjustment is necessary; G-CSF at the discretion of the centre's researcher
Grade 3 (500749)	Immediately reduce the dose by UN* one level and administer G-CSF at the discretion of the center investigator. If neutropenia disappears, the dose may be increased at the discretion of the center investigator.

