Grade 4 (<500)	Study weeks 1 and 2: defer or discontinue administration until grade 2 is reached, then resume administration with dose reduction of DOS* levels. Study weeks 3 to 48: defer or discontinue administration until grade 2 is reached, then resume administration with a dose reduction of ONE level. Administer G-CSF at the discretion of the centre's investigator. If neutropenia disappears, the dose may be increased at the discretion of the center investigator.

* The dose reduction levels of PEG-IFN are indicated in the label.

Treatment of IFN-associated thrombocytopenia

Table 2. Treatment of toxicity: decreased platelet count

Platelet count (cells/mm3)	MEASURE
Grade 2 (50,000-99,999)	No
Grade 3 (25,000-49,999)	Halving the dose of interferon
Grade 4 (<25,000)	Suspend the PEG-IFN definitively.

* The dose reduction levels of PEG-IFN are indicated in the label.

Dose reduction of PEG-IFN

Dose reductions should be uniform between participating centers and patients. For this purpose, the following reductions shall be used:

Table 3. Guidelines for Recommended Dose Reduction of PEG-IFN 1.5 µg/kg

		Reduction of one level (decrease to 1.0 µg/kg)			Two-level reduction (decrease to 0.5 µg/kg)		
		Volume			Volume		
Weight at Sit Up*		Pen Size	Injection (ml)	Dosage (µg)	Pen Size	Injection (ml)	Dosage (µg)
40 to 50 kg	88 to 110 lbs	Redipen 50	0,45	45	Redipen 50	0,30	30
>50 to 60 kg	>110 to 132 lbs	Redipen 80	0,35	56	Redipen 50	0,30	30
>60 to 65 kg	>132 to 143 lbs	Redipen 80	0,40	64	Redipen 50	0,35	35
>65 to 75 kg	>143 to 165 lbs	Redipen 80	0,45	72	Redipen 50	0,35	35
>75 to 80 kg	>165 to 176 lbs	Redipen 80	0,5	80	Redipen 50	0,40	40
>80 to 85 kg	>176 to 187 lbs	Redipen 120	0,35	84	Redipen 50	0,40	40

>85 to 95 kg	>187 to 209 lbs	Redipen 120	0,40	96	Redipen 50	0,50	50
>95 to 105 kg	>209 to 231 lbs	Redipen 150	0,35	105	Redipen 50	0,50	50
>105 to 125 kg	>231 to 275 lbs	Redipen 150	0,35	105	Redipen 50	0,50	50

* Use the usual rounding methods: values between 0.1 and 0.4 kg should be rounded down and those between 0.5 and 0.9 kg should be rounded up.

Missed or deferred doses of PEG-IFN

If a dose of PEG-IFN is delayed but is finally administered, the following guidelines are recommended for the following scheduled doses:

- Dose delay of 1 or 2 days: administer on the usual day of administration of the week (for example, if Monday is the usual day of administration and the dose is delayed to Wednesday, the next dose will be administered as usual, on Monday).

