11.3 Analysis

In this open study, all variables will be tabulated. Quantitative variables will be described by the number of available and omitted observations, the mean, the median, the standard deviation, the interval (minimum and maximum) and the first and third quartiles. Of the qualitative variables, the frequency and percentage will be presented. Omitted values will be tabulated with their frequency, but will not be included in the calculation of the percentages.

The primary endpoint will be assessed with a bilateral CI of 95% around the observed proportion of SVR. The analysis of the primary endpoint in SVR will be carried out in two ways. Patients who withdrew from the study within the first four weeks will be included in the main analysis, which will be counted as SVR failures. As a secondary analysis, an SVR analysis will also be performed, but restricted to patients who have not withdrawn from the study in the bitherapy period in the first four weeks. In both analyses, patients in whom SVR data are lacking due to premature withdrawal from the study at any time after the initial bitherapy period of the first four weeks will be included and counted as SVR failures.

Inferential analysis of boceprevir efficacy will be assessed by SVR at week 24 and the 95% confidence interval. A similar analysis will be applied to evaluate the secondary variables. For continuous quantitative variables, the mean or median and the 95% confidence interval or the interquartile interval shall be calculated.

Descriptive analyses of treatment-occurring adverse events and treatment-occurring adverse events that are possibly or likely related to the study drug will be performed. With regard to the safety assessment in the AEs, the 95% CI of the percentage of grade 3 or higher adverse events and other serious adverse events reported by the centres shall be provided. The highest grade episode per person over time will be used. Descriptive tables will be provided summarizing the events and the number of people who have presented the events by grade.

Variations in HIV-1 viral load or RNA and CD4+ T cell count at each post-enrollment visit will be summarized. The rates and reasons for premature discontinuation of treatment, including HCV treatment failures, will be summarized.

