In addition, a logistic regression analysis will be carried out taking SVR as a dependent variable. The importance of the previously identified prognostic factors will be confirmed by univariate logistic regression. The independence of these factors will then be evaluated using a stepwise method in which the factors that were significant in the univariate analyses will be used.

All analyses will be bilateral and will have a significance level of 5%. The following variables will be analyzed:

Efficacy: sustained virologic response, virologic response at weeks 4, 8, 12, and 24.

Safety: All adverse events, whether or not related to the study medication.

HCV resistance following BOC-containing treatment in patients with virologic failure.

* Predictive factors of SVR: SVR will be analyzed by subgroups according to sex, age, degree of fibrosis at baseline, previous null response, CD4 lymphocyte count at baseline, greater or lesser decrease of one logarithmic unit of HCV RNA at week 4, undetectable HCV RNA at week 8, and pharmacogenetic markers

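### The only named analysis population excludes patients with major deviations and no safety population is defined, so read literally the grade 3+ and serious-event percentages leave out some treated patients

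*Combined protocol and SAP*

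**What the plan says.** Section 11.7 describes a single population for the study: "all patients included in the study as detailed in the protocol and without major deviations from the protocol". It is not confined to efficacy, and the protocol does not say what makes a deviation major.

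Section 11.3 sets out the safety analysis. For adverse events, "the 95% CI of the percentage of grade 3 or higher adverse events and other serious adverse events reported by the centres shall be provided", taking each person's worst grade. No denominator is given. The list of variables later in 11.3 reads "Safety: All adverse events, whether or not related to the study medication". The same section does say who is counted in the two SVR analyses: withdrawals in the first four weeks are failures in the main analysis and left out of the secondary one, and later withdrawals are failures in both. Those rules are written for SVR only.

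On the role of safety, section 5 (and 1.10.1) states: "The primary objective of this study is to evaluate the safety and efficacy of response-guided therapy". Sections 1.13.2 and 6.1 list safety among the secondary endpoints, and section 11.2 words the primary objective as estimating SVR.

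**The concern.** A per-person percentage needs a denominator, and the only one the plan supplies is that of 11.7. Applied as written, it takes exposed patients out of both the numerator and the denominator of the toxicity percentages. The study has a single arm, so these absolute percentages are its main safety estimate and no control group shares the distortion. Because the trial is open-label and the term is undefined, nothing in the plan prevents deviations from being classed as major after the adverse events are known.

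The percentages are biased downward if deviators have more toxicity than other patients. The protocol offers several plausible routes:

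- **Contraindicated co-medication.** Section 8.2: "The administration of treatments that are contraindicated with the study drugs will not be allowed".
- **A directed peginterferon change that was not made.** Section 10.3 says of grade 3 neutropenia "Immediately reduce the dose by UN* one level", requires deferral or interruption at grade 4, and says of grade 4 thrombocytopenia "Suspend the PEG-IFN definitively". A patient who misses such a step already has a grade 3 or 4 laboratory abnormality. Section 10.1 treats a clinically important abnormality that requires a dose change as an adverse event, and grade IV abnormalities as serious.
- **A boceprevir dose reduction for intolerance.** Section 6.3: "The dose of BOC cannot be reduced in the study".
- **Enrolment against a safety-related exclusion,** such as platelets below 80,000/mm³ (section 7.2).

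The bias could also be nil or reversed, for example if deviators mainly took less drug. Stopping a drug for toxicity under the protocol's rules is not a deviation, so those patients stay in.

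**Working it through.** **Which text sets the denominator?**

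| Text | What it settles | Sets the safety denominator? |
|---|---|---|
| 11.7 | Patients in the study's analysis population | Yes, the only one named; excludes major deviators |
| 11.3, SVR rules | Handling of withdrawals for SVR | No, efficacy only |
| 11.3, adverse-event analyses | Treatment-emergent and centre-reported events; worst grade per person | No |
| 11.3, variable list | Events counted whatever their relation to treatment | No |
| 10.1 and 10.2 | Events to be recorded and notified | No |

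Only 11.7 says which patients are analysed for safety, and nothing exempts safety from it.

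**The plan's own figure.** Section 11.2 gives 128 patients for 60% ± 8.5 points with a two-sided 95% interval: 1.96² × 0.60 × 0.40 / 0.085² = 127.6, rounded up to 128. This reproduces and is not in dispute. It serves below as the number treated.

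**Size of the shift.** Let *e* be the number of treated patients excluded, *r* the deviators' risk of a grade 3+ or serious event, and 20% the risk in the others. The 20%, *e* and *r* are assumptions.

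- Plan's figure: 20.0%.
- All-treated figure: [*e* × *r* + (128 − *e*) × 0.20] / 128.
- Shift (all-treated minus plan): (*e*/128) × (*r* − 0.20).

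| Excluded | *r* = 10% | *r* = 20% | *r* = 40% | *r* = 60% |
|---|---|---|---|---|
| 6 (about 5%) | 19.5% | 20.0% | 20.9% | 21.9% |
| 13 (about 10%) | 19.0% | 20.0% | 22.0% | 24.1% |
| 19 (about 15%) | 18.5% | 20.0% | 23.0% | 25.9% |

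Worked entry: (13 × 0.60 + 115 × 0.20)/128 = (7.8 + 23.0)/128 = 24.1%. The shift spans (19/128) × (−0.10) = −1.5 points to (19/128) × 0.40 = +5.9 points. With 13 excluded, each 10-point difference in risk moves the result by 1.0 point.

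**Against sampling error.** With 115 patients and 20% observed, the 95% half-width is 1.96 × √(0.20 × 0.80/115) = 7.3 points.

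**Second set of assumptions.** With about 30% risk in non-deviators and whole-number counts:

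- 13 deviators: the 11.7 population gives 34/115 = 29.6%. All treated gives 38/128 = 29.7%, 40/128 = 31.3% or 43/128 = 33.6% if the deviators' risk is 30%, 50% or 70%.
- 26 deviators: 31/102 = 30.4%, against 39/128 = 30.5%, 44/128 = 34.4% or 49/128 = 38.3%.

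Here the understatement runs from about 0 to 8 points.

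**The case against.** The strongest reply is that this is an ambiguity rather than an exclusion. Section 11.3 sets its own inclusion rules for SVR, so it does not treat 11.7 as the last word. Its safety text speaks of treatment-emergent events and of serious events reported by the centres, and 10.2 has centres report every serious event with no exception for deviators. An analyst could take that to mean all treated patients. That reading is sensible, but none of those phrases says whose events enter the percentage, and adopting it departs from 11.7, which under 11.6 has to be justified in the report.

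Several other points stand and limit the weight of the finding:

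- The documents disagree on whether safety is primary: section 11.2 names SVR alone, and the sample size rests on SVR precision.
- The safety analysis is descriptive, with no hypothesis, threshold or interim look, and all events are collected, so nothing is lost for good.
- Because a major deviation is undefined, none of the listed routes is known to lead to exclusion. Missed peginterferon changes may be weak candidates, since the dose-reduction table in 10.3 is headed as recommended guidance.
- The assumed risks reach 40 points above the base rate but only 10 below, which tilts the range towards understatement. With no events at all among 19 deviators, the shift would be (19/128) × (−0.20) = −3.0 points.

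**Conclusion.** The concern holds. On its plain wording the plan removes treated patients with major deviations from the grade 3+ and serious-event percentages, and no other text restores them. Neither the direction nor the size of the effect can be established from the documents. Under the stated assumptions (20% base risk, 5% to 15% excluded, deviator risk 10% to 60%) the all-treated percentage differs from the reported one by −1.5 to +5.9 points. The shift is smaller than the 7.3-point half-width, so it would not overturn a broad reading of tolerability. It is systematic, however, and the interval does not allow for it. This should be fixed, but it does not threaten the trial's SVR result. Confidence is medium, because the practical effect depends on how many deviations are called major and on those patients' risk.

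**What to change.** Add one sentence to 11.7: *All safety analyses use every patient who received at least one dose of any study treatment, regardless of protocol deviations.* Report the boceprevir-exposed patients alongside as a subset, since everyone starts with four weeks of peginterferon and ribavirin alone; this is a useful addition rather than something the defect itself requires. Limit any exclusion for major deviations to a supportive efficacy analysis.

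The sentence can go into the same revision of 11.7 that settles the SVR population. It needs no new data, because 10.1 and 10.2 already require every adverse event to be recorded. The only cost is that the reported toxicity percentage may be slightly less favourable.
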